12.7 Clinical Laboratory Tests

Safety laboratory assessments will be conducted as specified in Schedule of Assessments (Section 18).

All laboratory tests, values, units, normal ranges, flags collected in the clinical database (i.e., results that are outside the normal ranges will be flagged with "L" (below normal range) or "H" (above normal range)) will be included in the-patient listings for further medical review.

For laboratory analysis, baseline will be defined as either the screening visit or the Cycle 1 Day 1 visit; whichever is the closest visit prior to the administration of study treatment.

12.7.1 CTCAE Grading

For the hematology laboratory tests of interest where CTCAE [version 5.0] severity criteria are specified, CTCAE severity grades will be assigned. These laboratory tests include:

| Panel | Test | CTCAE grade directions |
|------------|----------------|------------------------|
| Hematology | ANC | Decrease |
| | Hemoglobin | Decrease / Increase |
| | Platelet Count | Decrease |

| | | |
|--|------------------------------|----------|
| | White Blood Cell (WBC) count | Decrease |
| | Lymphocyte Count | Decrease |

Analyses will be performed using “shift tables” of CTCAE toxicity grades relative to the baseline (pre-treatment) toxicity grade. The number and proportion of patients with directional shifts of the “worst” CTCAE toxicity grade post-baseline and CTCAE toxicity grade of the last post-baseline visit relative to the baseline (pre-treatment) toxicity grade will be summarized for the selected hematology and chemistry parameters.

The CTCAE toxicity grading algorithms for the appropriate laboratory analytes are detailed in Section 19.

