7.5.6. Management of Hepatotoxic Risk

Investigators should monitor the patient for elevated levels of AST and/or ALT concurrent with abnormal elevations in total bilirubin that meet the criteria outlined below in the absence of other causes of liver injury and investigational treatment should be stopped as they are considered potential cases of drug-induced liver injury (DILI).

The following laboratory values should be evaluated for Hy's Law cases taking into consideration specific clinical symptoms of the patient and evaluation of other causes of hepatic impairment:

- Aminotransferases (AT), ALT or AST elevation > 3 times the upper limit of normal (ULN); AND
- Total bilirubin (TBL) > 2 times ULN, without initial findings of cholestasis (elevated serum alkaline phosphatase); AND

- No other immediately apparent possible causes of AT elevation and hyperbilirubinemia, including but not limited to viral hepatitis, pre-existing chronic or acute liver disease, or the administration of other drug(s) known to be hepatotoxic.

Patients with labs that are suspicious of DILI should return to the clinic as soon as possible, or at least within 48 hours, to be evaluated with laboratory tests, a detailed history and physical assessment.

The possibility of other causes for elevated liver function tests should be evaluated. Further testing for acute hepatitis A, B, or C infection and liver imaging (e.g., biliary tract) at a minimum may be warranted.

If on the repeat laboratory testing for drug induce liver injury (DILI), results continue to meet the threshold listed above, and after a thorough evaluation for alternative explanations fail to provide a clear clinical explanation, the ongoing hepatic injury, per protocol, the diagnosis should be DILI. ALL investigational treatment should be stopped as they are considered potential cases of drug-induced liver injury.

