12.7.3 Chemistry

Chemistry laboratory tests are planned to include Sodium, Potassium, Glucose, Calcium (Total), Creatinine, Protein (Total), Albumin, Bilirubin (Total), Bilirubin (Direct), Alkaline Phosphatase (ALP), Aspartate Aminotransferase (AST), Alanine Aminotransferase (ALT), Lipase, Amylase.

Due to the large number of laboratory visits, the data will be summarized by these post-baseline timepoint descriptors: First post-baseline, Last post-baseline value, Minimum post-baseline value, Maximum post-baseline value, and Average post-baseline value.

These chemistry laboratory test results are measured on a continuous scale and the observed values as well as changes from baseline values will be summarized for each

expansion group using n, mean, standard deviation, median, minimum and maximum values.

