19. CTCAE TOXICITY LABORATORY GRADING CHART

| Panel | Analyte | Type | Standard Unit | Directional Change of Interest | Toxicity Grades (CTCAE v5.0) |
|------------|------------------|----------------------------|-------------------------|--------------------------------|--|
| Hematology | WBC count | WBC with differential | 10 ⁹ /L | Decrease | Grade 0: \geq LLN Grade 1: $< \text{LLN} - 3.0 \times 10^9/\text{L}$ Grade 2: $< 3.0 - 2.0 \times 10^9/\text{L}$ Grade 3: $< 2.0 - 1.0 \times 10^9/\text{L}$ Grade 4: $< 1.0 \times 10^9/\text{L}$ |
| Hematology | ANC | WBC with differential | 10 ⁹ cells/L | Decrease | Grade 0: \geq LLN Grade 1: $< \text{LLN} - 1.5 \times 10^9/\text{L}$ Grade 2: $< 1.5 - 1.0 \times 10^9/\text{L}$ Grade 3: $< 1.0 - 0.5 \times 10^9/\text{L}$ Grade 4: $< 0.5 \times 10^9/\text{L}$ |
| Hematology | Lymphocyte count | WBC with differential | 10 ⁹ cells/L | Decrease | Grade 0: \geq LLN Grade 1: $< \text{LLN} - 0.8 \times 10^9/\text{L}$ Grade 2: $< 0.8 - 0.5 \times 10^9/\text{L}$ Grade 3: $< 0.5 - 0.2 \times 10^9/\text{L}$ Grade 4: $< 0.2 \times 10^9/\text{L}$ |
| Hematology | Hemoglobin | Erythrocytes and Platelets | g/L | Increase | Grade 0: \leq ULN Grade 1: $> 20 \text{ g/L} + \text{ULN}$ Grade 2: $> 20 - 40 \text{ g/L} + \text{ULN}$ Grade 3: $> 40 + \text{ULN}$ Grade 4: Not defined |
| | | | g/L | Decrease | Grade 0: \geq LLN Grade 1: $< \text{LLN} - 100 \text{ g/L}$ Grade 2: $< 100 - 80 \text{ g/L}$ Grade 3: < 80 Grade 4: Not defined |
| Hematology | Platelet count | Erythrocytes and Platelets | 10 ⁹ /L | Decrease | Grade 0: \geq LLN Grade 1: $< \text{LLN} - 75 \times 10^9/\text{L}$ Grade 2: $< 75 - 50 \times 10^9/\text{L}$ Grade 3: $< 50 - 25 \times 10^9/\text{L}$ Grade 4: $< 25 \times 10^9/\text{L}$ |

LLN=lower limit of normal. ULN=upper limit of normal.

The LLN and ULN for each analyte will be determined from the normal range of the local laboratory facility.

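### The Phase 2a SAP promises CTCAE shift tables for chemistry without grading any chemistry test, and no planned laboratory table counts patients who meet the protocol's joint thresholds for potential liver injury

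*SAP*

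**What the plan says.** Phase 2a SAP 12.7.1 limits grading to one panel: "For the hematology laboratory tests of interest where CTCAE [version 5.0] severity criteria are specified, CTCAE severity grades will be assigned". It then lists ANC, hemoglobin, platelets, white cells and lymphocytes. Its next paragraph widens the scope, because the grade shifts "relative to the baseline (pre-treatment) toxicity grade will be summarized for the selected hematology and chemistry parameters". For the cut-offs it points to one place: "The CTCAE toxicity grading algorithms for the appropriate laboratory analytes are detailed in Section 19". That section, headed "CTCAE TOXICITY LABORATORY GRADING CHART", has hematology rows only. Its footnote states that "The LLN and ULN for each analyte will be determined from the normal range of the local laboratory facility".

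SAP 12.7.3 lists 14 chemistry tests. It says "Due to the large number of laboratory visits, the data will be summarized by these post-baseline timepoint descriptors" (first, last, minimum, maximum and average), and "These chemistry laboratory test results are measured on a continuous scale and the observed values as well as changes from baseline values will be summarized" by n, mean, standard deviation, median, minimum and maximum.

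Protocol 7.5.6 sets a joint criterion for potential DILI. The first part is "ALT or AST elevation > 3 times the upper limit of normal (ULN); AND". The others are total bilirubin above 2 times ULN without initial signs of cholestasis, and no other evident cause.

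The Phase 1 SAP has the same text in 12.7.1 and the same hematology-only chart.

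**The concern.** There are two linked problems. First, the SAP commits to an output that its own grading rules cannot generate. A programmer would have to invent the chemistry selection and cut-offs or silently drop the table.

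Second, the chemistry summaries that can be produced look at one test at a time, without reference to ULN. The protocol's liver criterion is a property of one patient across two tests, expressed in multiples of ULN. Single-test summaries on the raw scale cannot recover it.

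Change from baseline in laboratory parameters is part of the Phase 2a primary endpoint (protocol 2.2.2.1). The laboratory tables of a primary safety endpoint would therefore not show how many patients crossed thresholds that the protocol itself singles out.

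**Working it through.** The plan states no figure on this point, so there is none to reproduce. The check sets the sections side by side and then tests what the planned statistics can distinguish.

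**1. Tests graded against tests promised**

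| Item | Source | Count |
|---|---|---|
| Tests listed for grading | SAP 12.7.1 | 5, all hematology |
| Tests with cut-offs | SAP Section 19 | 5, all hematology (hemoglobin in both directions) |
| Chemistry tests named | SAP 12.7.3 | 14 |
| Of these, in the Phase 2a panel | Protocol 6.13.2 | 12 (no lipase or amylase) |
| Chemistry tests graded | SAP 12.7.1 and Section 19 | 0 |

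**2. Other planned outputs that might give a joint count**

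- Adverse events of special interest (SAP 12.5) do not include liver injury.
- Dose-limiting toxicities are excluded from Phase 2a (SAP 12.6).
- Protocol 8.4.1 promises only descriptive changes from baseline.
- DILI appears in the Phase 2a SAP only in the abbreviation list.
- Listings show each value with its normal range and a high or low flag (SAP 12.7), but no multiple of ULN and no count.
- The treatment-emergent adverse event tables (SAP 12.1) count a hepatic event by preferred term if the investigator reports one.

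**3. What single-test summaries can tell**

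Let a patients exceed 3 times ULN for ALT or AST and b exceed 2 times ULN for bilirubin, out of N. The number with both lies between max(0, a + b − N) and min(a, b). Taking a = 3, b = 2 and N = 26 (the full size of Group 3a) as an illustration gives max(0, −21) = 0 and min(3, 2) = 2. The margins allow 0, 1 or 2 joint cases.

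Invented data for 26 patients make the same point. The values are peaks in multiples of ULN, with one ALT peak of 6 and one bilirubin peak of 3.

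| | Both peaks in one patient | Peaks in two patients |
|---|---|---|
| ALT: mean / SD / median / min / max | 1.1158 / 1.0532 / 0.86 / 0.33 / 6.0 | identical |
| Bilirubin: mean / SD / median / min / max | 0.715 / 0.4944 / 0.665 / 0.32 / 3.0 | identical |
| Patients over both thresholds | 1 | 0 |

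This holds generally. Exchanging two patients' complete bilirubin records within a group leaves every single-test statistic unchanged, including change from baseline, while the joint count can change.

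**4. Would there be anything to count?**

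The documents give no rate for joint elevations, so the rates here are assumptions. The chance of at least one case is 1 − (1 − p)^n. The planned total is n = 46 + 22 + 26 = 94.

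| Assumed p | n = 94 | n = 26 (Group 3a) |
|---|---|---|
| 1% | 61% | 23% |
| 2% | 85% | 41% |
| 5% | 99% | 74% |

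**5. Role of baseline**

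Protocol 4.1.1 admits patients with AST and ALT up to 3.0 times ULN. A patient can therefore enter at the edge of the transaminase threshold, and a post-baseline count needs the baseline value beside it.

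**The case against.** The strongest reply is that protocol 7.5.6 is a monitoring and management rule, not an endpoint. Its diagnosis needs repeat testing and the exclusion of other causes, which is clinical judgement. Liver injury is neither an endpoint nor an event of special interest. Protocol 8.4.1 promises descriptive changes from baseline, and SAP 12.7.3 delivers them. Nonclinical studies showed no liver injury (protocol 1.2.1). On this view the only true contradiction is the reference to chemistry in 12.7.1, and deleting it would resolve that.

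Much of this stands. The missing joint table breaks no explicit commitment, and the laboratory thresholds mark potential cases only. Deleting the reference would restore consistency, but it would leave the chemistry part of a primary safety endpoint without grades or any ULN-based display.

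A reader might infer that liver injury would go uncounted altogether. The documents do not support that. Protocol 7.1.1 treats clinically significant laboratory abnormalities as adverse events, and reported events reach the SAP 12.1 and 12.2 tables. Stopped treatment would appear among the reasons for discontinuation (SAP 10.2), and all values are listed. A reader might also infer that a large ALT rise would be hidden in a group mean. It would not, because 12.7.3 also tabulates the maximum. Only the link between the two tests in one patient is lost.

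There is one limit on this check. SAP 8.4 says that table shells form part of the SAP, but they are not in the text available, so the absence of a joint table is verified against the narrative only.

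**Conclusion.** The point holds in a bounded form. The chemistry shift table promised in Phase 2a SAP 12.7.1 cannot be built: 0 of 14 named chemistry tests, or 0 of the 12 in the Phase 2a panel, have a grade. No laboratory table described in the SAP counts patients over both biochemical thresholds for potential DILI. The planned statistics are the same whether such a patient exists or two patients each have one isolated rise.

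This should be corrected, but it does not invalidate the safety analysis, because listings and reported adverse events remain as routes to the cases. Neither route is a systematic count at the protocol's thresholds. The conclusion rests on the SAP narrative without its shells. The numerical examples use invented data and assumed rates.

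**What to change.** In the Phase 2a SAP, whose footer shows draft version 0.1:

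- Add CTCAE v5.0 rows to 12.7.1 and Section 19 for at least ALT, AST, alkaline phosphatase, total bilirubin and creatinine, so that the promised shift table exists.
- Add one patient-level table by expansion group. It should give the number of patients with ALT or AST above 3 times the local ULN, with total bilirubin above 2 times the local ULN, and with both within a stated time window. Without a window, peaks from different cycles would count as concurrent. Show alkaline phosphatase and baseline values alongside.
- State that this table uses scheduled and unscheduled results. SAP 8.4 and 9.5.3 admit unscheduled values to summaries that are not time-specific, but the general text of Section 9 is unclear.
- Label the patients as potential cases, since the absence of another cause needs clinical review.
- Confirm that total bilirubin is always collected. Protocol 6.13.2 allows total, direct or both, and the criterion needs total.

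The Phase 1 SAP has been executed (Phase 2a SAP, Section 1). For Phase 1, provide the same table as an additional analysis documented in the clinical study report.

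The cost is a few grading rows and one extra table. The planned chemistry data suffice if total bilirubin is available. The thresholds are the protocol's own, and no clinical rule changes.

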12.7.2 Hematology

Hematology laboratory tests are planned to include Hemoglobin, Hematocrit, MCV, Platelets, Absolute White Blood Count, Absolute Neutrophil Count, Absolute Lymphocyte Count, Absolute Monocyte Count, Absolute Eosinophils Count, Absolute Basophils Count, % Neutrophils, % Lymphocyte, % Monocytes, % Eosinophils, and % Basophils.

Due to the large number of laboratory visits, the data will be summarized by these post-baseline timepoint descriptors: First post-baseline, Last post-baseline value, Minimum post-baseline value, Maximum post-baseline value, and Average post-baseline value.

These hematology laboratory test results are measured on a continuous scale and the observed values as well as changes from baseline values will be summarized for each expansion group using n, mean, standard deviation, median, minimum and maximum values.

12.7.3 Chemistry

Chemistry laboratory tests are planned to include Sodium, Potassium, Glucose, Calcium (Total), Creatinine, Protein (Total), Albumin, Bilirubin (Total), Bilirubin (Direct), Alkaline Phosphatase (ALP), Aspartate Aminotransferase (AST), Alanine Aminotransferase (ALT), Lipase, Amylase.

Due to the large number of laboratory visits, the data will be summarized by these post-baseline timepoint descriptors: First post-baseline, Last post-baseline value, Minimum post-baseline value, Maximum post-baseline value, and Average post-baseline value.

These chemistry laboratory test results are measured on a continuous scale and the observed values as well as changes from baseline values will be summarized for each

expansion group using n, mean, standard deviation, median, minimum and maximum values.

12.7.4 Coagulation

Coagulation laboratory tests are planned to include Prothrombin Time (PT), Activated Partial Thromboplastin Time (aPTT), Thrombin Time (TT) and INR.

Due to the large number of laboratory visits, the data will be summarized by these post-baseline timepoint descriptors: First post-baseline, Last post-baseline value, Minimum post-baseline value, Maximum post-baseline value, and Average post-baseline value.

These coagulation laboratory test results are measured on a continuous scale and the observed values as well as changes from baseline values will be summarized for each expansion group using n, mean, standard deviation, median, minimum and maximum values.

12.7.5 Urinalysis

All Urinalysis test results (Protein, Blood, Specific Gravity, Glucose) will be presented in the patient listings.

12.8 Vital Signs and Weight

The vital sign tests to be collected include:

- Blood pressure (systolic and diastolic [mmHg])
- Heart rate (beats per minute [bpm])
- Respiratory rate (bpm)
- Temperature (c)
- Weight (lbs) once per cycle
- Height (in) at screening only.

See Schedule of Assessments (Section 18) for specific vital sign data collection timepoints.

Vital sign assessments measured on a quantitative scale will be summarized in a descriptive manner by calculating the n, mean, standard deviation, median, and range at the baseline timepoint (defined as either the screening visit or the Cycle 1 Day 1 visit; whichever is the closest visit prior to the administration of study treatment) and subsequent post-baseline timepoint, and by expansion group. Mean change from baseline will also be presented in the same manner.

Due to the large number of vital sign visits, the data will be summarized by these post-baseline timepoint descriptors:

- First post-baseline, Last post-baseline value, Minimum post-baseline value, Maximum post-baseline value, and Average post-baseline value.
- Height will only be summarized at baseline.

All vital sign tests will be included in patient listings for further medical review.

12.9 12-Lead Electrocardiogram (ECG)

The 12-Lead ECG assessments include:

- Heart Rate
- QT interval
- PR interval
- QRS interval
- QTcF interval

See Schedule of Assessments (Section 18) for specific ECG data collection timepoints. In summary they include:

- Screening.
- On Day 1 of each cycle ECGs will be performed both pre and post SQP33 protodrug infusion.
- On Days 2-5 of Cycle 1 ECGs will be performed post SQP33 protodrug infusion only.

Quantitative Analysis:

ECG assessments measured on a quantitative scale will be summarized in a descriptive manner by calculating the n, mean, standard deviation, median, and range at the baseline timepoint (defined as either the screening visit or the Cycle 1 Day 1 visit; whichever is the closest visit prior to the administration of study treatment) and subsequent post-baseline timepoint, and by expansion group. Mean change from baseline will also be presented in the same manner.

Categorical Analysis:

Additionally, QTcF results will also be categorized according to their values into the categories as defined in ICH E14:

- ≤ 450 ms
- > 450 ms to ≤ 480 ms
- > 480 ms to ≤ 500 ms
- > 500 ms

and categorized according to their change from baseline into the categories:

- ≤ 30 ms,
- > 30 ms to ≤ 60 ms
- > 60 ms

The categories described above will be summarized in frequency tables using number of patients (n) and percentages at each post-dose timepoint for each expansion group.

A separate analysis of the overall ECG interpretation (categorical: Normal, Abnormal Not Clinically Significant, and Abnormal Clinically Significant) will be performed using “shift tables” relative to the baseline (screening) interpretation. The number and proportion of patients with directional shifts of ECG interpretation categories post-baseline relative to the baseline (screening) will be summarized.

All ECG results will be included in patient listings for further medical review. Of specific interest would be the interpretation of Abnormal, Clinically Significant ECG panel.

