6.6.2. Phase 2a Expansion Groups

Routine Dosing Vitals: Vital signs as outlined below should be obtained on IP administration Days 1 to 5 (or Day 1 to 3 for the 3-day treatment Group 2 patients)

Routine Vital Time Points Dosing Days 1-5	
Pre-infusion	
Immediately post-infusion (+ 5 min)	
Prior to Discharge from treatment site	

Cycle 1 Day 1 Only Dosing Vital Signs: Vital signs as outlined below should be obtained on IP administration Cycle 1 Day 1 only:

Cycle 1 Day 1* Vital Signs Time Points	
In Relation to Administering	Vitals Time Points
SQL70 biopolymer	Pre-SQL70 injection
SQP33 protodrug	Pre-SQP33 infusion Immediately post-SQP33 infusion (+ 5 min)
	Prior to Discharge from treatment site

*Day 2-5 of Cycle 1 vital signs time points should follow the routine dosing vitals

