APPENDIX J – SCHEDULE OF ASSESSMENTS – EXPANSION GROUP 2: UNRESECTABLE STS (3 DAY)

Study Day	Screening	Treatment				SFTY FU	LTFU
		Week 1			Week 2		
		Day 1 ^a	Day 2	Day 3	Day 10 ± 2 days		
On-Site	On-Site	On-Site	On-Site	On-Site	Telephone or On-Site ^b	On-site	Variable ^m
Screening	Informed consent ^c	X					
	Medical history	X					
	Review Inc/Exc Criteria	X					
	Confirm Eligibility		X				
Safety	Physical Exam	X					
	Symptom-Directed PE		X ^d			X	
	Vital Signs	X	X	X	X	X	
	ECHO or MUGA	X	Every other cycle ^e			X ^k	
	Triplecate 12-Lead ECG	X	X ^{d, f}	Cycle 1 Only	Cycle 1 Only	X	
	ECOG	X	Cycle 2+			X	
	AE Review		X	X	X	X	
Labs	Conmed Review	X	X	X	X	X	
	Hematology & Chemistry	X	X ^d	Cycle 1 Only	X	Cycle 1 Only ^d	X ^d
	Coagulation & Urinalysis	X					X ^d
	Pregnancy Test	X ^g	X ^d				X ^d
	Serology	X					
	Plasma PK		See Separate PK Schedule				
	PBMC / ctDNA		Cycle 1, 2, 3 ^o				
IP	Cardio Tox Biomarkers	X	Every other cycle ^e			X	
	Tumor Biopsy		Cycle 1, 2, 3 only ^h				
Survival	CT / MRI & RECIST	X	Every 6 weeks ⁱ			X ^l	X ⁿ
	Administer SQL70 Biopolymer		X				
	Administer SQP33 Protodrug		X ^j	X	X		
Vital Status							X

Notes For APPENDIX J – Schedule of Assessments –EXPANSION GROUP 2: UNRESECTABLE (3 DAY)

- A - Day 1-3 can begin on any day that allows for the completion of the three consecutive treatments within the week.
- B - Day 10 visit may be performed via telephone (using a lab closer to a patient's home) or on-site.
- C - Written informed consent must be obtained prior to any study-specific procedures.
- D - May be performed up to 3 days before the visit.
- E - ECHO/MUGA to be performed every other cycle starting at Cycle 3; may be performed up to 7 days before the visit. Serum sample for cardiotoxicity biomarker analysis is to be collected on the same day.
- F - ECG to be performed pre dose and post dose +30 minutes.
- G - To be collected \leq 7 days prior to Cycle 1 Day 1 for women of child-bearing potential.
- H - Collect optional biopsy unless the tumor is considered too small to be biopsied; biopsy can be performed during screening and up to 4 days prior to Day 1 for other cycles.
- I - May be performed up to 7 days prior to the projected every 6 weeks from C1D1 date.
- J - SQP33 protodrug infusion occurs within 3 hrs \pm 30 mins after receiving SQL70 biopolymer injection.
- K - ECHO or MUGA not required at the Safety Follow-Up visit if performed in the previous 14 days.

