3. PHASE 2A EXPANSION OBJECTIVES AND ENDPOINTS

3.1 Primary Objectives

Further investigate the safety and tolerability profile of SQ3370 in anthracycline naïve patients with:

- Group 1: Neo-adjuvant treatment of patients with STS of the extremity who are ineligible for primary surgical resection and under consideration for possible/probable amputation, with predefined anthracycline sensitive tumors.
- Group 2: Patients with unresectable, locally advanced or metastatic STS, with predefined anthracycline sensitive tumors and compare safety and tolerability of the RP2D in two infusion schedules of SQP33 (3-day vs 5-day).
- Group 3a Patients with relapsed or metastatic squamous-cell head and neck cancer

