3.5 Efficacy Endpoints

- Objective response rate (ORR) per Response Evaluation Criteria in Solid Tumors (RECIST) v1.1.
- Overall Survival (OS)
- Time from enrollment to first subsequent therapy (TFST)
- Plasma concentration and PK parameters for SQP33 protodrug and active Dox following SQ3370 treatment.
- Group 1: Advanced High-risk Soft Tissue Sarcoma of the Extremity
 - Histopathological Response
 - Surgical outcome amputation/limb-salvage vs planned
 - Disease-free survival
 - Local recurrence-free survival [Time Frame: 2 years]
 - Distant recurrence-free survival
 - Symptomatic disease control
- Group 2: Comparison of the RP2D of SQ33 total dose in mg/m² administered every 21 days administered over 3 vs over 5 days
 - Compare safety and tolerability of two infusion schedules of SQP33 (3-day vs 5- day)
 - Pharmacokinetic comparison of the two infusion schedules
 - PFS per RECIST v1.1
 - DoR per RECIST v1.1
 - DCR per RECIST v1.1
- Group 3a: Head & Neck
 - DoR per RECIST v1.1
 - PFS per RECIST v1.1
 - Time to local-regional progression or distant progression per RECIST v1.1
 - Local-regional control per RECIST v1.1
 - DCR per RECIST v1.1

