8. DATA PRESENTATION AND HANDLING

8.1 Table and Individual Patient Data Listing Considerations

Summary tables and listings will be prepared according to ICH Guideline E3 (as appropriate for a Phase 2A study).

In general, summary tables will be organized with respect to the Phase 2A expansion groups:

- Group 1: Extremity STS
- Group 2: Unresectable STS 3-Day Infusion
- Group 2: Unresectable STS 5-Day Infusion
- Group 3A: Head and Neck
- Total

Row entries in post text tables are made only if data exists for at least one patient (e.g., a row with all zeros will not appear). The only exception to this rule will apply to tables that summarize the study termination status of patients (e.g., reasons for not completing the study). In this case, zeros will appear for study termination reasons that no patient satisfied. The summary tables will clearly indicate the number of patients to which the data apply and unknown or not performed are distinguished from missing data.

Summary tables for any concomitant medications will be coded according to the World Health Organization (WHO) Drug dictionary September 2020 (or later). Adverse event preferred terms and body/organ systems and medical history conditions will be coded using the Medical Dictionary for Regulatory Activities (MedDRA®) dictionary Version 24.1 (or later).

Listings will also be sorted by expansion group (where applicable) and patient number. Listings will also include visit number, visit date/time and days relative to the initiation of study treatment.

In general, missing data will not be imputed unless otherwise specified. Any imputed or derived data will be flagged in the individual patient data listings. Imputed data will not be incorporated into any raw or primary datasets. These data will be retained in derived analysis datasets.

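### Group 2 minimum, maximum and worst-grade safety summaries are not like-for-like, because the 5-day arm is measured on two more days (vital signs in every cycle, hematology and chemistry in Cycle 1 only)

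*SAP*

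**What the plan says.** Comparing the two Group 2 schedules on safety is part of the Phase 2a primary objective (SAP 3.1: "compare safety and tolerability of the RP2D in two infusion schedules of SQP33 (3-day vs 5-day") and is listed again among the Group 2 endpoints (SAP 3.5: "Compare safety and tolerability of two infusion schedules of SQP33"). Change from baseline in vital signs and laboratory parameters belongs to the Phase 2a primary endpoint (Protocol 2.2.2.1). SAP 8.1 gives "Group 2: Unresectable STS 3-Day Infusion" its own column, and 8.5 places it next to the 5-day column.

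For hematology, SAP 12.7.2 states: "Due to the large number of laboratory visits, the data will be summarized by these post-baseline timepoint descriptors". The descriptors, as SAP 12.8 also lists them for vital signs, are "First post-baseline, Last post-baseline value, Minimum post-baseline value, Maximum post-baseline value, and Average post-baseline value". Chemistry (12.7.3) and coagulation (12.7.4) use the same five. SAP 12.7.1 adds shift tables based on the worst post-baseline CTCAE grade. Nothing restricts these summaries to days that both schedules share.

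The measurement days follow the infusions. Under Protocol 6.6.2, routine vital signs "should be obtained on IP administration Days 1 to 5 (or Day 1 to 3 for the 3-day treatment Group 2 patients", with three timepoints on each such day. Appendices I (5-day) and J (3-day) set the laboratory days. SAP 12.8 sends the reader to SAP Section 18 for timepoints, but Section 18 prints only the 5-day Group 2 schedule. The difference is therefore visible only in the protocol.

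**The concern.** An expected maximum rises, and an expected minimum falls, as more readings are taken, even when the underlying distribution is unchanged. If one column draws its extremes from more days than the other, the two differ for a reason unrelated to tolerability. Here the column with more days is the 5-day schedule. Other things equal, its extremes are wider and the 3-day column looks a little calmer. The 3-day arm receives 40% of the cycle dose on each of Days 2 and 3, against 20% in the 5-day arm (Protocol Table 2), and its tolerability is the question Group 2 is asking. With up to 11 patients per arm and no randomization (SAP 5), a systematic artefact is better kept out of the comparison.

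**Working it through.** The plan states no figure on this point, so there is none to reproduce.

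**Inputs.** Let k be the number of cycles given (up to 12, Protocol 3.1.4.3). Post-baseline scheduled days:

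- Vital signs (Protocol 6.6.2; Appendices I and J): every infusion day plus safety follow-up, so 5k + 1 days on 5-day and 3k + 1 on 3-day.
- Hematology and chemistry, 5-day (Appendix I): Cycle 1 Days 2, 3, 4, 5 and 10; Days 1 and 5 of each later cycle; safety follow-up. 5 + 2(k − 1) + 1 = 2k + 4.
- Hematology and chemistry, 3-day (Appendix J): Cycle 1 Days 2, 3 and 10; Days 1 and 3 of each later cycle; safety follow-up. 3 + 2(k − 1) + 1 = 2k + 2.
- Coagulation: safety follow-up only after screening, 1 against 1.

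**Assumption.** The documents give no within-patient SD or correlation. Results are therefore in within-patient SD units, with identical normal distributions in both arms.

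**Formula.** For n independent standard normal values, E(max) = ∫ x · n · φ(x) · Φ(x)^(n−1) dx. The minimum is the mirror image.

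| k | Vital-sign days, 5-day / 3-day | E(max) | Gap | Lab days, 5-day / 3-day | E(max) | Gap |
|---|---|---|---|---|---|---|
| 1 | 6 / 4 | 1.267 / 1.029 | 0.24 | 6 / 4 | 1.267 / 1.029 | 0.24 |
| 2 | 11 / 7 | 1.586 / 1.352 | 0.23 | 8 / 6 | 1.424 / 1.267 | 0.16 |
| 4 | 21 / 13 | 1.889 / 1.668 | 0.22 | 12 / 10 | 1.629 / 1.539 | 0.09 |
| 12 | 61 / 37 | 2.326 / 2.129 | 0.20 | 28 / 26 | 2.014 / 1.982 | 0.03 |

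**Sensitivity, vital signs.**

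- Counting readings instead of days, one cycle has 3 × 5 = 15 against 3 × 3 = 9. E(max) is 1.736 against 1.485, a gap of 0.25. With safety follow-up added (15k + 1 against 9k + 1), the gap is 0.23 at one cycle, 0.20 at four and 0.18 at twelve.
- Simulating 200,000 patients over four cycles with exchangeable within-cycle correlation gives a gap of about 0.17 SD at correlation 0.5 and 0.11-0.12 SD at 0.8.
- In the same simulations the difference in the average is 0.00 SD.

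**Sensitivity, hematology.** Protocol 1.1 puts the myelosuppression peak of conventional doxorubicin at 10 to 14 days, and both arms have the Cycle 1 Day 10 draw. If that value lies 2 SD below the others, the four-cycle gap in the minimum falls from 0.09 to 0.03 SD. At 3 SD below, it falls to 0.01 SD.

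**After restriction to shared days.** Vital signs use 3k + 1 days in each arm, and hematology and chemistry use k + 3 in each. The count-driven gap is then 0.

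**The case against.** The strongest reply is that little depends on these columns. The tables are descriptive, and no test is attached to them. The Group 2 stopping criterion rests on related Grade ≥3 anemia and febrile neutropenia events (SAP 4). Clinically significant laboratory abnormalities are also captured as adverse events, and all values are listed. This stands and limits the point to a modest one. It does not remove it: these changes are part of the primary endpoint, and the SRC reviews all available safety data at 6 patients per arm after about two cycles (SAP 7.1). If these summaries were used then, the independent-day gaps would be 0.23 SD for vital signs and 0.16 SD for laboratory tests.

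A second reply is that the two further infusions belong to the 5-day regimen, so part of any wider range is real exposure. That also stands, and is why the all-readings table should remain.

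A reader might go further in three ways that the documents do not support.

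- *All five descriptors favour the 3-day arm.* The average, first and last values, weight and coagulation have no count bias. An average can shift through which days are sampled, but the documents do not fix the direction.
- *The laboratory imbalance runs through every cycle.* From Cycle 2 both arms have two laboratory days per cycle. What remains is a timing difference, Day 5 against Day 3.
- *The 3-day arm misses a definable share of threshold crossings.* Taking an assumed 1-5% chance per reading, 1 − (1 − p)^n gives 14-54% with 15 readings and 9-37% with 9, a shortfall of 31-38%. The documents supply no such risk. The sum also needs independent readings and equal risk on days with no infusion.

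**Conclusion.** The point holds for minimum and maximum vital signs in all cycles. It also holds for minimum and maximum hematology and chemistry and for worst hematology grade, where the count imbalance arises only in Cycle 1 and is diluted as cycles accrue. With identical true distributions, the 5-day vital-sign extremes are wider by about 0.20-0.25 within-patient SD under independence, and by about 0.1-0.2 SD with exchangeable correlation of 0.5-0.8. The hematology and chemistry gap is about 0.24 SD at one cycle, 0.09 at four and 0.03 at twelve, and smaller for hematologic minima if the shared Day 10 draw sets them.

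These sizes assume normal readings, equal numbers of cycles in the two arms and scheduled readings only. It would be tempting to conclude that the 3-day schedule must look safer by construction. The documents support only a modest tilt in that direction, other things equal. A real effect of the larger Day 2 and Day 3 infusions, unequal numbers of cycles, or unscheduled readings (which SAP 8.4 admits to these summaries) could outweigh it.

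**What to change.** In SAP 12.7.1-12.7.3 and 12.8, for the two Group 2 columns, present the minimum, maximum and worst-grade summaries on days scheduled in both arms:

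- Vital signs: Days 1-3 of each cycle and safety follow-up.
- Hematology and chemistry: Cycle 1 Days 2, 3 and 10, Day 1 of each later cycle, and safety follow-up.

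Keep the all-readings version alongside, so that Day 4-5 data stay visible. Days 1-3 are preferable to pairing Day 3 with Day 5 as the last infusion day: that pairing would keep a timing mismatch and drop Day 2, the first of the 3-day arm's larger infusions.

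The cost is SAP wording, one programming flag and one extra set of tables, with no new visits or samples. The common-day version omits Day 4-5 readings and the later-cycle Day 3 and Day 5 laboratory draws. The Phase 2a SAP is still marked version 0.1, so the change can be pre-specified.
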